7.4.7.2 PPE Treatment

- Treatment may begin at the first clinical signs of PPE. At first occurrence, independent of grade, supportive measures should be promptly initiated.
- Tender areas should be protected as follows:
 - Use socks/gloves to cover moisturizing creams
 - Wear well-padded footwear; use insole cushions or inserts.
 - Foot soaks with tepid water and Epson salts.
- Creams may be used as follows:
 - Non-urea based creams may be applied liberally.
 - Keratolytic creams (eg, urea-based creams 10%, salicylic acid 6%) may be used on affected (hyperkeratotic) areas 3 times per day.
 - Alpha hydroxyl acids (AHA)-based creams may be applied liberally 2 times a day. Approximately 5% to 8% provides gentle chemical exfoliation.
 - Topical analgesics (eg, lidocaine 2%) may be used for pain control.
 - Topical corticosteroids like clobetasol 0.05% should be considered for patients with grade 2 or 3 PPE. Systemic steroids should be avoided.

Use of Celecoxib

A meta-analysis of PPE prevention strategies concluded that celecoxib, with statistically significant results, was the most promising agent (1). Therefore, celecoxib is recommended to reduce the severity of sorafenib-related PPE as follows:

- Celecoxib 200 mg once daily should begin at the first clinical signs or symptoms of grade 2 PPE.

Guidelines for sorafenib dosing modifications are listed in Section 7.

7.4.8 QT Prolongation Considerations

7.4.8.1 ECGs will be evaluated for QTc prolongation prior to next scheduled treatment

7.4.8.2 Any time QTc is evaluated during the course of the study:

- When HR is between 60-100 bpm, no manual read of QT required
- When HR < 60 or > 100 bpm, manual read of QT by cardiologist is required, using Fridericia correction

Any questions or concerns about ECG readings will be reviewed with a cardiologist.

7.4.8.3 To the extent possible, concurrent use of drugs known to cause clinically significant QT prolongation should be avoided. Such drugs may be identified at the Credible Meds website (<http://crediblemeds.org/login>). The Credible Meds website requires free user registration to view the list of clinically relevant QT prolonging drugs, eg, those known to carry a risk of causing Torsades de Pointes (TdP). QT prolonging drugs to be avoided during this trial are shown in the Credible Meds list of “drugs with known TdP risk.”

7.4.8.4 When concurrent use of sorafenib and any drug on the Credible Meds list of “drugs with known TdP risk” cannot be avoided, review QTc prior to concurrent use. If pre-concurrent use QTc is:

- grade 0 (< 450 ms), follow-up QTc evaluation should be done at the next scheduled follow-up visit.
- grade 1 (450-480 ms), follow-up QTc evaluation should be done within 8 days after concurrent use starts.
- grade 2 (481-500 ms), withhold sorafenib until follow-up ECG at next possible opportunity shows QTc grade 1 or less (≤ 480 ms); evaluate QTc within 8 days after reintroduction of sorafenib.

7.4.8.5 Any new onset of dysrhythmia on ECG during study treatment phase will be reviewed and managed with input from cardiology.

7.4.8.6 For any episode of syncope (grade 3) or near syncope (pre-syncope grade 2) or QTc grade 3 or greater (> 500 ms on 2 ECGs), see Section [7.1.1](#).

7.5 Laboratory Monitoring and Clinical Exam

Patients in the safety lead-in cohort (for qualifying toxicity assessment) will be seen weekly for the first 4 weeks of combination study therapy, then every 2 weeks for the next 4 weeks, and then monthly. Visits for subsequently enrolled patients are required every 2 weeks for the first 8 weeks, then monthly. Assessments to be done at each visit are as shown in the [Study Calendar](#). Serum valproic acid levels will be monitored every 2 weeks, or more frequently as clinically indicated through the end of cycle 2. After cycle 2 they will be checked as clinically indicated. Determination of steroid dose will be made at least

every 2 weeks (weekly in the safety lead-in cohort) and steroid dose may be tapered at the treating physician's discretion if the patient demonstrates a stable to improved neurologic exam.

In the event that a patient complains of abdominal pain, serum amylase and lipase will also be checked. Severe abdominal pain warrants a CT scan of the abdomen to rule out visceral perforation and pancreatitis.

7.6 Duration of Therapy

A cycle is defined as 4 weeks. Treatment will continue for the duration of response or stable disease.

Study treatment continues until one of the following:

- Investigator determination that discontinuation is in a patient's best medical interest
- Progression
- Withdrawal of support of study sponsor

The reason for study treatment discontinuation and the date treatment was discontinued must be documented in the OnCore CRF.

7.7 Monitoring Patient Compliance

A drug diary will be provided to each patient to use to track study drug administration. The diary will be reviewed by the study team periodically (see [Study Calendar](#)). Patient reports of self-administration, review of medication diary and pill counts will be used to assess study medication compliance. Concurrent medication assessments will be used to capture corticosteroid use and supportive care medications.

7.8 Duration of Follow Up

Patients who discontinue treatment **for any reason other than death or their choice to withdraw from all study follow-up** remain on study in follow-up status for an initial 30-day AE evaluation period following the last dose of study agent(s). This 30-day post-treatment follow-up period is meant to capture resolution or stabilization of ongoing treatment-related AEs or evolution of new treatment-related AEs.

The initial AE follow-up period may be extended if new or worsening treatment-related AEs require longer observation. Similarly, the initial AE follow-up period may end early in the event of death, patient request to withdraw from follow-up, or initiation of new anti-cancer therapy.

After the initial AE follow-up period, patients who are not evaluable for objective response (see Section [10.1](#)) are off study. Patients who are evaluable for objective response enter an extended follow-up period for progression and/or survival outcomes.

Patients who discontinue treatment with an ongoing response (PR or CR) or with ongoing stable disease (SD) are followed until the first evidence of progression after coming off treatment or until other anti-cancer therapy is initiated. At the onset of progression or

initiation of new therapy, whether this occurs during the initial or extended follow-up period, patients are followed only for survival.

The primary reasons for a patient's discontinuation from study treatment and from follow-up status are to be recorded in the source documents and the CRFs.

Certain late-occurring AEs may be subject to reporting during the extended follow-up period (eg, secondary malignancies).

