2.2 Secondary Objectives

2.2.1 Determine the efficacy of the combination of sorafenib, valproic acid, and sildenafil, in terms of 6-month PFS in high-grade glioma patients who are evaluable for response and who have tumors that express PDGFR α .

2.2.2 Evaluate the overall response rate, based on Response Assessment in Neuro-Oncology (RANO) criteria or Macdonald criteria, to the drug combination in patients

who are evaluable for response (those who express PDGFR α and those who do not).

- 2.2.3 Evaluate the overall response rate, based on RANO or Macdonald criteria, to the drug combination in PDGFR α expressing tumors in patients who are evaluable for response.
- 2.2.4 Determine the efficacy of the drug combination, in terms of 12-month survival and median overall survival in patients who are evaluable for response (those who express PDGFR α and those who do not).
- 2.2.5 Determine the efficacy of the drug combination, in terms of 12-month survival and median overall survival in high-grade glioma patients who are evaluable for response and who have tumors that express PDGFR α .
- 2.2.6 Evaluate the safety and toxicity of the drug combination.

■ [REDACTED]

■ [REDACTED]

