3.3 Secondary Endpoints

- 3.3.1 Proportion of patients evaluable for response, with tumors that express PDGFR α , with 6-month PFS defined as the time from the first day a patient receives study treatment until time of progression per RANO or Macdonald criteria or death, whichever occurs first.
- 3.3.2 Overall response rate (CR+PR), using RANO or Macdonald criteria, in patients evaluable for response regardless of tumor PDGFR status

- 3.3.3 Overall response rate (CR+PR), using RANO or Macdonald criteria, in patients who are evaluable for response and who have tumors that express PDGFR α .
- 3.3.4 Proportion of patients evaluable for response, regardless of tumor PDGFR status, who are alive at 12 months after the first day a patient receives study treatment. OS defined as the time from the first day a patient receives study treatment until death by any cause.
- 3.3.5 Proportion of patients evaluable for response with tumors that express PDGFR α who are alive at 12 months after the first day a patient receives study treatment. OS defined as the time from the first day a patient receives study treatment until death by any cause.
- 3.3.6 AEs using NCI Common Terminology Criteria for Adverse Events, Version 4.0 (CTCAE v4.0).

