10 MEASUREMENT OF EFFECT

10.1 Definitions

Evaluable for toxicity. All patients will be evaluable for toxicity from the time of their first treatment with sorafenib and/or valproic acid and/or sildenafil.

Evaluable for qualifying toxicities for the safety lead-in. Only those patients who have completed the first cycle of therapy (or have experienced a qualifying toxicity prior to the end of the first cycle) will be evaluable for the safety lead-in. Qualifying toxicities will be defined in the first cycle only. Patients must have completed twice-daily sorafenib dosing for at least 21 out of the first 28 days to be considered to have had sufficient exposure to the regimen for qualifying toxicity evaluation. Patients who are not evaluable for the qualifying toxicity assessment for the safety lead-in will be replaced.

Evaluable for qualifying toxicities for the early stopping rule after the safety lead-in. Patients who have initiated the first cycle of therapy will be considered evaluable for the early stopping rule. Qualifying toxicities will be defined in the first cycle only. Patients who are not evaluable for the qualifying toxicity assessment for the early stopping rule will not be replaced unless they were included in the safety-lead in.

Evaluable for objective response. Patients who have been treated with the combination of twice-daily sorafenib and valproic acid for a minimum of 28 days, and have had their disease re-evaluated, will be considered evaluable for response. These patients will have their response classified according to the definitions stated below. Patients who do not complete study dosing for at least 28 days, or those who do not have their disease re-evaluated following initiation of the combination of sorafenib and valproic acid, will be replaced to ensure that a sufficient number of patients will be available for response evaluation.

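### Overall survival is counted from first dose only in patients who lived long enough to become response-evaluable, and Section 7.8 stops survival follow-up for everyone else about 30 days after their last dose

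*Combined protocol and SAP*

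**What the plan says.** **Follow-up (Section 7.8).** Every patient who stops treatment has an adverse-event period of 30 days after last dose. It can be longer: "The initial AE follow-up period may be extended if new or worsening treatment-related AEs require longer observation". It can also be shorter, on death, withdrawal from follow-up or new anti-cancer therapy. After it, "patients who are not evaluable for objective response" are off study. By contrast, "Patients who are evaluable for objective response enter an extended follow-up period for progression and/or survival outcomes". Note K of the study calendar collects survival status about every 2 months, in extended follow-up only.

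**Analysis set (Section 10.1).** Response-evaluable means at least 28 days of twice-daily sorafenib with valproic acid, plus a disease re-evaluation. Patients who do not complete 28 days, or "those who do not have their disease re-evaluated following initiation of the combination of sorafenib and valproic acid, will be replaced". Section 10.4 schedules re-evaluation every 8 weeks and permits earlier imaging if progression is suspected.

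**Endpoint.** Section 2.2.4 asks for "12-month survival and median overall survival in patients who are evaluable for response", and 2.2.5 asks the same in PDGFRα-expressing tumors. Sections 3.3.4 and 3.3.5 both give the time origin: "OS defined as the time from the first day a patient receives study treatment until death by any cause".

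**Analysis (Section 13.5).** Kaplan-Meier estimates of OS with 95% intervals. No landmark, delayed entry or all-treated sensitivity analysis is described.

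**The concern.** Whether a patient belongs to the survival set is settled by what happens after time zero. A patient who dies on day 15 is replaced and never enters the OS estimate. A patient who dies on day 60 after a scan enters it, with the first four weeks or more credited as time at risk in which death could not have been counted. This is guaranteed (immortal) survival time, and it pushes the median and the 12-month proportion upward whatever the treatment does.

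The follow-up rule adds a second problem. Survival status needs no scan, so lack of response evaluability is no reason to stop collecting it. A patient who stops on day 20 for toxicity is observed to about day 50 (20 + 30) and then leaves, even if alive and willing to be followed. Patients who stop early for toxicity or decline are unlikely to be a random subset.

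At stake is whether the reported 12-month survival and median OS describe the patients who were treated. The analysis set can be changed at the end of the trial; survival status that was never collected may not be obtainable then.

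**Working it through.** **The plan's own figures.** No sample size, power or target is stated for OS. The only formal design is the Simon two-stage rule for 6-month PFS in Section 13.2 (4 or more of 16 to continue, 11 or more of 33 for success; 20% against 40%). It reproduces by exact binomial calculation: one-sided type I error 0.0475 and power 0.811. OS plays no part in it.

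**Inputs**
- Median survival after recurrence (Section 1.1): 25-30 weeks for grade IV, 39-47 weeks for grade III. The grade IV midpoint is (25 + 30)/2 = 27.5 weeks.
- Guaranteed survival L: 4 weeks (28-day minimum, Section 10.1) or 8 weeks (first scheduled re-evaluation, Section 10.4).
- Assumptions, not in the documents: exponential survival; 12 months = 52.2 weeks.

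**Formulas**, for median m in weeks:
- S(t) = 0.5^(t/m)
- Share dying before L: 1 − S(L)
- 12-month survival among those alive at L: S(52.2)/S(L) = 0.5^((52.2 − L)/m)
- Median from first dose among those alive at L: m + L

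**At the 27.5-week midpoint**
- Deaths before week 4: 1 − 0.5^(4/27.5) = 9.6%. Before week 8: 1 − 0.5^(8/27.5) = 18.3%.
- All treated: median 27.5 weeks; 12-month survival 0.5^(52.2/27.5) = 26.8%.
- L = 4: median 31.5 weeks; 12-month survival 0.5^(48.2/27.5) = 29.7%.
- L = 8: median 35.5 weeks; 12-month survival 0.5^(44.2/27.5) = 32.8%.

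**Across the protocol's medians**

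| Median (weeks) | 12-month survival, all treated | Alive at week 4 | Alive at week 8 |
|---|---|---|---|
| 25 | 23.5% | 26.3% | 29.4% |
| 30 | 29.9% | 32.8% | 36.0% |
| 39 | 39.5% | 42.5% | 45.6% |
| 47 | 46.3% | 49.1% | 52.1% |

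The shift is about 3 points at 4 weeks and about 6 at 8 weeks, for grade III as for grade IV.

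**What the mandated data would leave unknown.** Let q be the non-evaluable share and s the 12-month survival in evaluable patients. If nothing is known at 12 months about the non-evaluable, all-treated 12-month survival lies between (1 − q)s and (1 − q)s + q. The documents do not give q. With s = 30% assumed:
- q = 10%: 27% to 37%
- q = 20%: 24% to 44%
- q = 30%: 21% to 51%

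Deaths recorded on treatment or in the 30-day window would lower the upper ends.

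**The case against.** **The restriction is declared.** Sections 2.2, 3.3 and 7.8 agree on the response-evaluable set, so this is not a hidden inconsistency. That stands, but disclosure does not remove the bias.

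**Early deaths are recorded for everyone.** Section 8.4 records adverse events through 30 days after treatment for all patients, Section 8.1.2 makes death a serious event, and the calendar has a survival entry in the initial 30-day period. This stands. A reader might infer that all-treated survival is lost altogether; the documents do not support that. A Kaplan-Meier curve in all treated patients could be drawn, with early leavers censored about 30 days after last dose. What remains is that this censoring may be informative and that their 12-month status is not in protocol-mandated data.

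**The 8-week figure is an upper case.** A reader might take the 29% longer median (8/27.5) as the expected bias. Unscheduled imaging is allowed, so a declining patient can qualify from about week 4, and only the 4-week minimum follows from the definition.

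**The effect is small beside sampling error.** With 33 patients, the 95% half-width at 26.8% is 1.96 × √(0.268 × 0.732/33), or about 15 points. True, but the bias has one direction and does not shrink with more patients.

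**Other text in Section 7.8 may already cover it.** The section also says that at progression or new therapy, in either the initial or the extended period, follow-up continues for survival alone. That sentence sits in the paragraph on patients who stop with ongoing response or stable disease, so it probably does not override the off-study sentence. The two need reconciling either way.

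**Conclusion.** The point holds as a bias and data-collection weakness in a secondary, descriptive endpoint, and it should be corrected. Response-evaluable OS measured from first dose contains at least about 4 weeks of guaranteed survival. Under exponential survival and the protocol's own medians, this adds 4 weeks to the median and about 3 points to 12-month survival with no drug effect; the upper case is 8 weeks and about 6 points. These sizes depend on constant hazard. The eligibility limits (ECOG 0-2 and laboratory thresholds) may make very early deaths rarer than the model implies, while loss of patients who stop early for toxicity or decline could add to the bias.

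Two further inferences go beyond the documents. One is that the trial's OS will be overstated by a known amount against the 5.6-9.6 months cited in Section 1.7: the protocol does not describe the populations or time origins behind that range, and no formal OS comparison is planned, so one can say only that comparability is uncertain. The other is that this point undermines the go/no-go decision, which rests on 6-month PFS alone.

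**What to change.** 1. **Section 7.8 and note K.** Follow every patient who received study treatment for survival status, about every 2 months, until death or withdrawal from follow-up, including after new anti-cancer therapy. Leave progression follow-up and imaging rules as they are. Reword the off-study sentence and the sentence on survival-only follow-up so that they agree.
2. **Sections 2.2.4, 2.2.5, 3.3.4, 3.3.5 and 13.5.** Make OS and 12-month survival from first dose in all treated patients the main analysis; for 2.2.5 and 3.3.5, in all treated patients with PDGFRα-expressing tumors. All five places must change together, or the objectives will contradict the endpoints.
3. **Response-evaluable set.** Keep it as supportive, starting the clock at a landmark fixed in advance and including only patients alive and already evaluable at that time.

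**Cost.** A few more status checks, with no added visits or scans. To reach 33 evaluable patients with an assumed non-evaluable share of 10%, 20% or 30%, 33/(1 − q) gives 37, 42 or 48 treated patients, so 4 to 15 more people to follow. Note L already requires archived tissue, so PDGFRα status needs no new sampling. The reported survival will look less favourable.

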8 ADVERSE EVENTS: DEFINITIONS AND REPORTING REQUIREMENTS

8.1 Definitions

8.1.1 Adverse Event (AE)

AE means any untoward medical occurrence associated with the use of a drug in humans, whether or not considered drug related.

8.1.2 Serious Adverse Event (SAE)

An AE is considered "serious" if in the view of the investigator, it results in any of the following outcomes:

- death,
- a life-threatening AE (An AE is considered "life-threatening" if, in the view of either the investigator or sponsor, its occurrence places the patient or subject at immediate risk of death. It does not include an AE that, had it occurred in a more severe form, might have caused death.),
- inpatient hospitalization or prolongation of existing hospitalization,
- a persistent or significant disability/incapacity or substantial disruption of the ability to conduct normal life functions, or
- a congenital anomaly/birth defect.

Important medical events that may not result in death, be life-threatening, or require hospitalization may be considered serious when, based upon appropriate medical judgment; they may require medical or surgical intervention to prevent one of the outcomes listed in this definition.

8.1.3 Unanticipated Problem (UP)

UPs include any incident, experience, or outcome that meets all of the following criteria:

- unexpected (in terms of nature, severity, frequency) given (a) the research procedures that are described in the protocol-related documents; such as the IRB-approved research protocol and informed consent document; and (b) the characteristics of the subject population being studied;

- related or possibly related to participation in the research (ie, there is a reasonable possibility that the incident, experience, or outcome may have been caused by the procedures involved in the research; and
- suggests that the research places subjects or others at a greater risk of harm (including physical, psychological, economic, or social harm) than was previously known or recognized.

8.2 Adverse Event Characteristics

8.2.1 **CTCAE term (AE description) and grade:** The descriptions and grading scales found in the revised NCI CTCAE version 4.0 will be utilized for AE reporting. All appropriate treatment areas should have access to a copy of the CTCAE version 4.0. A copy of the CTCAE version 4 can be downloaded from the CTEP website: http://ctep.cancer.gov/protocolDevelopment/electronic_applications/ctc.htm.

8.2.2 **Expectedness:** AEs can be 'Unexpected' or 'Expected'.

Unexpected AEs are those AEs occurring in one or more subjects participating in the research protocol, the nature, severity, or frequency of which is not consistent with either:

- The known or foreseeable risk of AEs associated with the procedures involved in the research that are described in (a) the protocol-related document, such as the IRB-approved research protocol, any applicable investigator brochure, and the current IRB-approved informed consent document, and (b) other relevant sources of information, such as product labeling and package inserts;

or

- The expected natural progression of any underlying disease, disorder, or condition of the subject(s) experiencing the AE and the subject's predisposing risk factor profile for the AE.

See Sections [9.1.9](#) (sorafenib), [9.2.8](#) (valproic acid), and [9.3.10](#) (sildenafil).

8.2.3 **Attribution** of the AE:

- Definite – The AE *is clearly related* to the study treatment.
- Probable – The AE *is likely related* to the study treatment.
- Possible – The AE *may be related* to the study treatment.
- Unlikely – The AE *is doubtfully related* to the study treatment.
- Unrelated – The AE *is clearly NOT related* to the study treatment.

